4.1.3. Multicenter Studies

For the purposes of covariate adjustment in the statistical analysis, countries will be grouped into regions. The following regions are defined:

- European (Czechia, France, Hungary, Italy, Poland, Spain)
- US
- Rest of World (Australia, Canada, Puerto Rico, Japan, Taiwan)

If there are insufficient subjects in each region for the statistical procedures to converge satisfactorily, the combining of regions will be considered.

4.1.4. Subgroups of Interest

Table 4 specifies the subgroups of interest to be used in summary or analyses and the subgroup categories.

Table 4Subgroups of Interest

Subgroup	Category	
Age 1	12-17, 18-64, >=65	
Age 2	12-17, >=18	
Age 3	12-17, 18-64, 65-74, >=75	
Gender	Male, Female	
Weight	4 categories determined by quartiles of weight at baseline from the study data	
Race	American Indian or Alaska Native, Asian , Black or African American, Native Hawaian or Other Pacific Islander, White, Mixed	
Region	European (Czechia, France, Hungary, Italy, Poland, Spain), US, Rest of the World (Australia, Canada, Puerto Rico, Japan, Taiwan)	
Baseline ICS Dose	Medium, High	
Baseline Eosinophil Supgroup 1	<0.15, >=0.15 cells/uL	
Baseline Eosinophil Subgroup 2	<0.30, >=0.30 cells/uL	
Baseline ACQ-5	<1.5, >=1.5	

Sample size may be small for some subgroup analyses. All sub-group statistical analysis results should be interpreted with caution, especially those with small sample size. If the number of participants is too small (ie. <20) within a category of a subgroup, then the categories may be refined or only summary statistics will be produced.

4.2. Primary Endpoint Analyses

4.2.1. Definition of endpoint

The primary endpoint is the annualized rate of clinically significant exacerbations over the 52 weeks following randomisation.

Clinically significant exacerbations of asthma are defined as worsening of asthma requiring the use of systemic corticosteroids (IM, IV or oral) and/or hospitalisation and/or ED visit (see protocol Section 8.2.2). For all participants, IV or oral steroids (e.g., prednisone) for at least 3 days or a single IM CS dose is required. For participants on maintenance systemic CSs, at least double the existing maintenance dose for at least 3 days is required.

Exacerbations recorded in the eCRF are considered as verified clinically significant exacerbations and will be included in the primary analysis.

Exacerbations separated by less than 7 days will be treated as a continuation of the same exacerbation.

4.2.2. Main analytical approach

Pri	mary Statistical Analyses
End	dpoint(s)
•	Annualized rate of clinically significant exacerbations over 52 weeks
Мо	del Specification
•	Generalized linear model assuming a negative binomial distribution
•	Terms in the model:
	 Response: number of recorded clinically significant exacerbations experienced per subject.
	 Categorical: treatment group, exacerbation history (variable (2, 3, 4+)), baseline ICS dose (medium, high), geographical region
	 Continuous: baseline pre-bronchodilator % predicted FEV1
	Offset: Log _e (total time in the study in years)
Мо	del Checking & Diagnostics
•	The fit of the regression models will be examined using "Q-Q" plots of the standardized residuals. Interpretation of these plots will be aided by the addition of simulation-generated tolerance boundaries.
Res	sults Presentation
•	Treatment group model estimated annualized exacerbation rates and associated 95% CI
•	pairwise treatment rate ratios and associated p-value and 95% CI.
•	pairwise treatment percent reductions in annual exacerbation rate and associated 95% CI
Hai	ndling of missing data and data excluded due to intercurrent events
•	For participants that discontinue study intervention due to reasons related to the COVID-19 pandemic, the observed data for the period following this intercurrent event will be excluded from the analysis. Data for this period will be assumed "missing at random" (MAR) (based on all data included in the analysis under the current estimand strategy).
•	For participants that withdraw from the study, preventing assessment of the primary endpoint, the data for the period following withdrawal will be assumed MAR (based on all data included in the analysis under the current estimand strategy).
Sul	bgroup Analysis
•	By baseline ICS dose (medium, high), by baseline eosinophil subgroup 1 (<0.15, >=0.15), by baseline eosinophil subgroup 2 (<0.30, >=0.30) and by baseline ACQ-5 (<1.5, >=1.5) subgroup analyses will be performed for FAS analysis set.
•	For subgroup analysis, subgroup, subgroup*treatment group and subgroup*visit*treatment group terms will be included in each of subgroup analysis model.

Primary Statistical Analyses
 In the event the subgroup analysis model fails to converge, model simplification methods may be
addressed (i.e. adjusting covariate structure, streamlining timepoints, combining subgroups, running
model separately for subgroup).
 A forest plot will be produced to present estimated treatment differences and 95% CIs at week 52
 including all subgroups (including P-value for subgroup*treatment group interaction)
Annualized rate of clinically significant exacerbations over each of 13 week interval will also be performed.

Additional Analysis

The same primary endpoint analysis will be performed using FAS-modified analysis set

4.2.3. Sensitivity analyses

For the main analytical approach, data that is missing due to study withdrawal is assumed to be missing at random. The aim of sensitivity analyses is to assess the robustness in the treatment effect and conclusion in the main analytical approach when departing from the missing at random assumption. Two sensitivity analyses will be performed for this investigation.

4.2.3.1. Sensitivity Analysis 1 (MNAR Based on off-treatment Data)

This sensitivity analysis will be performed where subjects who withdrew from the study early will have missing data imputed for the period of time between withdrawal from the study to the Week 52 visit based on the off-treatment data collected from subjects who continued in the study following discontinuation of randomised intervention. Multiple imputation methods will be used with results combined across imputations using Rubin's method [Roger, 2018].

If the total unobserved/excluded time in the study is <3% of the total study duration or if <50% of the total off-treatment period is observed then the sensitivity analysis will not be conducted.

4.2.3.2. Sensitivity Analysis 2 (Tipping Point Analysis)

Tipping point analysis will explore the impact of missing data by using differing assumptions regarding the exacerbation rate in subjects who withdraw from the study. Subjects who withdrew from study early will have missing data imputed for the period of time between withdrawal from the study to the Week 52 visit based on a range of values for the rate of exacerbations per year following study withdrawal. The values to be investigated will be based on increases relative to the estimated rates obtained within each arm under the MAR assumption. The imputed exacerbation rates will vary independently for the active and placebo arms, and will include scenarios where subjects in the active arm have worse outcomes following early withdrawal from the study than subjects in the placebo arm. The tipping point multiple imputation method will be based on pattern mixture models [Keene, 2014]. The results from the analyses of each sample are combined using Rubin's method.

If the test for the endpoint is not significant at the two-sided 5% level, then the sensitivity analysis for the endpoint will not be performed.

4.3. Secondary Endpoints Analyses

4.3.1. Definition of endpoint(s)

The secondary endpoints are:

- Change from baseline in SGRQ total score at Week 52
- Change from baseline in ACQ-5 score at Week 52
- Change from baseline in pre-bronchodilator FEV₁ at Week 52
- Change from baseline in ANSD at Week 52 (see Section 4.4.10)
- Change from baseline in ADSD at Week 52 (see Section 4.4.10)
- Annualised rate of exacerbations requiring hospitalisation and/or Emergency Department (ED) visit over 52 weeks

4.3.2. Main analytical approach for SGRQ total score, ACQ-5 score and pre-bronchodilator FEV₁

Secondary Endpoints Analyses
Endpoint(s)
 Change from baseline in SGRQ total score at Week 52 Change from baseline in ACQ-5 score at Week 52 Change from baseline in pre-bronchodilator FEV1 at Week 52
Model Specification
 Mixed Models Repeated Measures (MMRM) model. Terms in the model: Response: SGRQ Total score or ACQ-5 score or pre-bronchodilator FEV1 at each visit. Categorical: treatment group, exacerbation, baseline ICS dose (medium or high), exacerbation history (variable (2, 3, 4+)), geographical region, visit Continuous: baseline (SGRQ Total score, or ACQ-5 score, or baseline pre-bronchodilator FEV1), baseline pre-
 bronchodilator % predicted FEV1 (for SGRQ total score and ACQ-5 endpoints only) Interaction: baseline*visit, treatment group*visit Repeated: visit The MMRM analysis for SGRQ total scores will include data collected at Weeks 4, 12, 26, 40 and 52.
 The MMRM analysis for ACQ-5 score will include data collected at Weeks 2, 4, 8, 12, 16, 20, 24, 26, 28, 32, 36, 40, 44, 48 and 52. In the event the model fails to run due to too many assessment timepoints, timepoints included in the analysis may be reduced by keeping the timepoints of most interest. Suggested order for dropping timepoints is week 44, 20, 36, 16, 32, 8, 48, 24, 28.
 The MMRM analysis for pre-bronchodilator FEV1 will include data collected at Weeks 26 and 52. The model will be fit with an unstructured variance-covariance matrix.
 The Kenward and Roger method (KR) for approximating the denominator degrees of freedom and correcting for bias in the estimated variance-covariance of the fixed effects will be used. In the event the model fails to run using the KR method, then the residual method will be used instead. In the event the model fails to run using residual method and assessments are from many timepoints, timepoints included in the analysis may be reduced by keeping the timepoints/intervals of most interest. Baseline is defined in Section 4.1.2
 Two models will be fitted; one with a response variable of change from baseline and one with the response variable as the raw value.
Model Checking & Diagnostics
 Distributional assumptions underlying the model used for analysis will be examined by obtaining a normal probability plot of the residuals and a plot of the residuals versus the fitted values (i.e. checking the normality assumption and constant variance assumption of the model respectively) to gain confidence

that the model assumptions are reasonable.
Ilts Presentation
Least-square (LS) means and LS mean change from baseline values for each treatment group will be presented with their associated standard errors as well as 95% CIs. The estimated treatment difference along with corresponding standard error, 95% CI and P-values for each visit will be presented. The LS mean treatment differences (and associated 95% CIs) for all visits will also be presented graphically. SGRQ total scores, ACQ-5 score and pre-bronchodilator FEV1 (absolute value and changes from baseline) wil also be summarised by treatment group and visit.
Handling of missing data and data excluded due to intercurrent events
For participants that discontinue study intervention due to reasons related to the COVID-19 pandemic, the observed data for the period following this intercurrent event will be excluded from the analysis. Data for this period will be assumed MAR (based on all data included in the analysis under the current estimand strategy). For participants that withdraw from the study, preventing assessment of the endpoint, the data for the period
following withdrawal will be assumed MAR (using data collected under the proposed estimand strategy).
tional Analysis
same secondary endpoint analyses will be performed using FAS-modified analysis set
group Analysis by baseline eosinophil subgroup 1 (<0.15, >=0.15), by baseline eosinophil subgroup 2 (<0.30, >=0.30) and by baseline ACQ-5 (<1.5, >=1.5) subgroup analyses will be performed for FAS analysis set . For subgroup analysis, subgroup, subgroup*treatment group and subgroup*visit*treatment group terms will be included in each of subgroup analysis model.
In the event the subgroup analysis model fails to converge, model simplification methods may be addressed (i.e. adjusting covariate structure, streamlining timepoints, combining subgroups, running model separately for subgroup). A forest plot will be produced to present estimated treatment differences and 95% CIs at week 52 including all subgroups (including P-value for subgroup*treatment group interaction)

4.3.3. Main analytical approach for annualised rate of exacerbations requiring hospitalisation and/or ED visit over 52 weeks

The annualised rate of exacerbations requiring hospitalisation and/or ED visit over 52 weeks will be analysed using a negative binomial generalised linear model, as described for the primary endpoint, Section 4.2.2 for details. This endpoint would only be analysed in the event that a total of 20 or more exacerbations requiring hospitalisation and/or ED visit occurred in the study.

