9.4.3. Secondary Endpoints

9.4.3.1. Main Estimands

Target Participant Population	Adult and adolescent participants with severe uncontrolled asthma with an eosinophilic phenotype following the strategy outlined below for dealing with the main intercurrent events that are anticipated.
Secondary Endpoints	
 Change from baseline in SGRQ total score at Week 52 Change from baseline in ACQ-5 score at Week 52

	
 Change from baseline in pre-bronchodilator FEV₁ at Week 52
Intercurrent events and strategies	
The anticipated key intercurrent events and corresponding strategies:
 
 Study intervention discontinuation due to reasons unrelated to the COVID-19 pandemic: treatment policy strategy i.e. regardless of the intercurrent event occurring. Study intervention discontinuation due to reasons related to the COVID-19 pandemic: hypothetical strategy i.e. had the intercurrent event not occurred. Change in maintenance therapy or use of prohibited medications (listed in Section 6.9.2): treatment policy strategy i.e. regardless of the intercurrent event occurring
Summary measure	Difference in means between GSK3511294 + SoC and placebo + SoC.
Analysis Method	
The analysis will be performed using a repeated measures mixed model. Covariates included will be baseline, region, baseline maintenance OCS therapy (OCS vs. no OCS), baseline ICS dose (medium or high dose, see Appendix 10), number of exacerbations in the year prior to the study, baseline % predicted FEV₁, treatment group and visit, plus interaction terms for visit by baseline and visit by treatment group. The difference in means and 95% CI will be provided for the comparison between GSK3511294 + SoC and placebo + SoC.

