4. STATISTICAL ANALYSES

4.1. General Considerations

4.1.1. General Methodology

The Full Analysis Set (FAS) will be used for all Study Population, Efficacy, Immunogenicity and PD analyses, unless otherwise stated. The Safety analysis set will be used for safety analyses, unless otherwise stated. PK analysis sets will be used for PK data analysis. FAS-Japan, Safety-Japan and PK-Japan will be used for Japan outputs. The Output and Programming Specification (OPS) document will provide more details.

Confidence intervals will use 95% confidence intervals (CI) unless otherwise specified.

Unless otherwise specified, continuous data will be summarised using descriptive statistics: n, mean, standard deviation (std), median, minimum and maximum. Categorical data will be summarised as the number and percentage of participants in each category.

For endpoints that are formally modelled, summary statistics will be provided. In the statistical analysis where covariates are included in the modelling, the following approach will be applied:

- The covariate of exacerbation history is classified as 2, 3, 4+. In the event that exacerbation history is <2, it will be included in the category of '2'.
- For the covariate of baseline pre-bronchodilator % predicted FEV1, screening prebronchodilator % predicted FEV1 will be used if baseline value is missing. If both sreeening and baseline pre-bronchodilator % predicted FEV1 are missing, a missing value will be assigned for this covariate.

Where statistical models are used, if there are important departures from the distributional assumptions, transformations of covariates or alternative models may be explored as supporting analyses.

Randomisation is stratified based on baseline ICS dose (medium or high). All statistical models will include this stratum as a covariate. In the case of wrong stratification assigned at the time of randomization, the analyses will be performed based on the data collected in the CRF, not the assigned stratum at randomization.

Assessments collected at withdrawal visit will be included in summary tables but won't be included in any statistical analysis.

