4.1.2. Baseline Definition

Baseline values for visit based assessments and eDiary assessments are defined in Table 3.

Unless otherwise stated, if baseline is missing, no derivation will be performed and baseline will be set to missing.

Parameter	Study Assessments Collected Prior to Dosing		Baseline Definition	
	Screening (Visit 1)	Day 1 Pre-Dose (Visit 2)		
Efficacy, Health Outcom	nes and Other			
SGRQ total and domain		Х	Day 1 pre-dose	
scores				
ACQ-5		Х	Day 1 pre-dose	
Pre-bronchodilator FEV ₁	Х	X	Day 1 pre-dose	
Post-bronchodilator FEV ₁	Х	X	Day 1 pre-dose	
PROMIS Fatigue items score		X	Day 1 pre-dose	
ADSD/ANSD weekly mean score	X (daily following Screening)		Average of measurements from Day -7 to Day -1 inclusive (at least 4 days must be non-missing)	
Awakenings at night due to asthma symptoms requiring rescue medication use 2-week mean	X (daily followin	g Screening)	Average of measurements from Day -7 to Day -1 inclusive (at least 4 days must be non-missing)	
Morning PEF 2-week mean	X (daily followin	g Screening)	Average of measurements from Day -6 to Day 1(pre-dose) inclusive (at least 4 days must be non-missing)	
Daily asthma symptom scores 2-week mean	X (daily followin	g Screening)	Average of measurements from Day -6 to Day 1(pre-dose) inclusive (at least 4 days must be non-missing)	
Mean number of occasions of rescue medication use/day 2-week mean	X (daily followin	g Screening)	Average of measurements from Day -6 to Day 1(pre-dose) inclusive (at least 4 days must be non-missing)	
SNOT-22 score		Х	Day 1 pre-dose	
PGI-S	Х	Х	Day 1 pre-dose	
Safety				
Blood pressure	X	X	Values from most recent assessment prior to first dose of study treatment which records both systolic and diastolic BP	
Pulse rate	Х	X	Most recent individual value prior to first dose of study treatment	
Clinical Chemistry	Х	Х	Most recent individual value prior to first dose of study treatment	
ECG endpoints	Х	X	Values from most recent ECG conducted prior to first dose of study treatment	
Hematology with differential (including eosinophil count)	X	X	Most recent individual value prior to first dose of study treatment	
Other				
Complement C3 and C4		X	Day 1 pre-dose	
Immunogenicity		Х	Day 1 pre-dose	

Table 3Baseline Definitions & Derivations

NOTES :

- Only records that have been assigned a treatment phase of 'pre-treatment' will be considered as baseline assessments.
- ADSD is to be completed before going to bed and refers to asthma symptoms during the day. Day 1

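### The SAP leaves baseline % predicted FEV1 out of the pre-bronchodilator FEV1 model, where the protocol specifies it, and neither declares nor justifies the change

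*SAP*

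**What the plan says.** **Protocol 9.4.3.1** has a single analysis method for the three continuous secondary endpoints. Besides the endpoint's own baseline, region, maintenance OCS and ICS dose, the covariates include "number of exacerbations in the year prior to the study, baseline % predicted FEV₁, treatment group and visit". There is no exception for FEV1.

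**SAP 4.3.2** gives the continuous terms as "Continuous: baseline (SGRQ Total score, or ACQ-5 score, or baseline pre-bronchodilator FEV1"), followed by baseline pre-bronchodilator % "predicted FEV1 (for SGRQ total score and ACQ-5 endpoints only". The FEV1 model therefore holds treatment, ICS dose, exacerbation history, region, visit, baseline FEV1, and the interactions of visit with baseline and with treatment. It uses Weeks 26 and 52.

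**Declared changes.** SAP 4.12, which lists departures from protocol amendment 2, covers only ADSD/ANSD. The version history (SAP Table 1) records removal of the maintenance OCS covariate, with a reason. It has no entry for % predicted FEV1.

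**Missing baselines.** SAP 4.1.1 has a fallback for the % predicted covariate: "screening prebronchodilator % predicted FEV1 will be used if baseline value is missing". SAP Table 3 defines baseline FEV1 itself as Day 1 pre-dose, and the general rule in 4.1.2 is: "Unless otherwise stated, if baseline is missing, no derivation will be performed and baseline will be set to missing".

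**The concern.** Pre-bronchodilator FEV1 is step 4 of the seven-step fixed sequence in SAP 2.1, so its model supports a claim under type I error control. For such an endpoint the protocol and SAP should describe one model, and any difference should be listed with its reason. Here a reader comparing them finds two different confirmatory models.

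The omitted term also carries some information. Baseline FEV1 in the model is an absolute volume. Percent predicted scales it by what is expected for the participant's age, sex and height, none of which is a term in the model, and enrolment starts at age 12. Two participants with the same volume can differ in how far they fall below expected. Adjusting for that could remove some residual variance at almost no cost, since the variable is collected and already used in the primary, SGRQ and ACQ-5 models.

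**Working it through.** **1. Text comparison**

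| | SGRQ | ACQ-5 | Pre-BD FEV1 |
|---|---|---|---|
| Protocol 9.4.3.1: own baseline | yes | yes | yes |
| Protocol 9.4.3.1: % predicted FEV1 | yes | yes | yes |
| SAP 4.3.2: own baseline | yes | yes | yes |
| SAP 4.3.2: % predicted FEV1 | yes | yes | **no** |
| Listed in SAP 4.12 or version history | – | – | **no** |

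**2. The plan's own secondary power figures (SAP Table 6)**

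Inputs: 125 placebo, 250 active, two-sided 5%. Power = Φ(δ / (SD × √(1/125 + 1/250)) − 1.96), with √(1/125 + 1/250) = 0.1095.

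- SGRQ: 7 / (17 × 0.1095) = 3.76; Φ(1.80) = 96.4% (stated 96%).
- ACQ-5: 0.35 / (1.1 × 0.1095) = 2.90; Φ(0.94) = 82.8% (stated 83%).

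Both reproduce. The documents give no effect size, SD or power for FEV1, so there is no FEV1 figure to correct and the rest uses assumed ranges.

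**3. Precision from the omitted covariate**

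Let R² be the share of residual variance that % predicted explains once baseline FEV1 is in the model (assumed 1% to 5%). Including it multiplies the SE by √(1 − R²); the equivalent extra sample is 375/(1 − R²) − 375.

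| R² | SE factor | Equivalent extra participants |
|---|---|---|
| 1% | 0.995 | 4 |
| 3% | 0.985 | 12 |
| 5% | 0.975 | 20 |

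If power with the covariate is P (also assumed), power without it is Φ((1.96 + z_P) × √(1 − R²) − 1.96):

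| R² | from 90% | from 80% |
|---|---|---|
| 1% | 89.7% | 79.6% |
| 2% | 89.4% | 79.2% |
| 5% | 88.5% | 78.0% |

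**4. Simulation check (all inputs assumed)**

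This was a single-visit ANCOVA with 375 participants allocated 2:1 and 600 replicates per setting. Predicted FEV1 had mean 3.2 L and SD 0.7; % predicted had mean 58 and SD 15; measurement error SD was 0.15 L; further outcome noise SD was 0.40 L; the treatment effect was 0.1 L. The extra dependence of outcome on % predicted was 0, 0.05 or 0.1 L per 15 points.

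| Extra dependence | SE, baseline only | SE, plus % predicted | Reduction |
|---|---|---|---|
| 0 | 0.04656 | 0.04649 | 0.2% |
| 0.05 | 0.04650 | 0.04606 | 0.9% |
| 0.1 | 0.04649 | 0.04551 | 2.1% |

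Mean treatment estimates agreed closely (for example 0.1037 and 0.1036 in the first row): no shift.

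**5. Missing Day 1 FEV1**

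If 1%, 2% or 5% of 375 lacked a Day 1 value, that would be about 4, 8 or 19 participants, and the SE would rise 0.5%, 1.0% or 2.6% (factor 1/√(1 − m)). In the same simulation at 5% missing with no extra dependence, the SE was 0.0479 with those participants left out, 0.0467 with Visit 1 substituted and 0.0466 with complete data. The documents do not say how many values are missing.

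**The case against.** **The terms overlap.** Percent predicted comes from the same measurement as baseline FEV1, and volume in litres already reflects age, sex and height in part. The explicit wording in SAP 4.3.2 looks like a deliberate choice to avoid two versions of one variable. This stands as a reason to expect a small gain. It does not answer the main point: no reason is given, and the protocol had already put both terms in this model.

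**Participants lost at step 4.** A reader might infer that the SAP wrongly drops people with no Day 1 FEV1 although a Visit 1 value exists. It is true that "Two models will be fitted; one with a response variable of change from baseline and one with the response variable as the raw value", that both need the baseline, and that 4.1.1 rescues only the covariate. But Protocol 8.2.3 names Visit 2 as the baseline spirometry, so Day 1 agrees with the protocol. Filling a covariate leaves the outcome alone; replacing baseline FEV1 changes the change score itself. The Visit 1 value is also the one used for eligibility (Protocol 5.1), so regression to the mean would affect within-arm changes. Later spirometry is matched to the Visit 2 time of day, run-in may include a treated exacerbation (5.6), and retests are allowed (8.1.2), so the substitute is not even unique. Visit 2 is in person with spirometry scheduled, and no missing count is given. Absence before dosing should cost precision rather than cause bias.

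**Steps 5 to 7 at risk.** One might argue that lost precision endangers ANSD, ADSD and the hospitalisation/ED rate. With no FEV1 power stated, no shortfall is shown.

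**Conclusion.** The point holds as an undeclared and unexplained departure from the protocol in the step 4 model, with a small cost in precision. Across both checks, restoring the term lowers the SE by about 0.2% to 2.5%, and omitting it costs about 0 to 2 points of power. These sizes rest on an assumed partial R² of up to 5%, assumed simulation inputs and assumed reference powers of 80% and 90%; none comes from the documents. Nothing suggests bias or loss of type I error control.

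It should not be read as a protocol requirement for post-bronchodilator FEV1. Protocol 9.4.3.1 covers only the pre-bronchodilator endpoint; the post-bronchodilator one is among the other endpoints, whose analysis Protocol 9.4.4 leaves to the SAP.

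**What to change.** In SAP 4.3.2, delete the restriction on baseline pre-bronchodilator % predicted FEV1, so that the pre-bronchodilator FEV1 model includes it as Protocol 9.4.3.1 specifies. Post-bronchodilator FEV1 then follows through SAP 4.4.4, although the protocol does not require it there. The deletion also settles whether the ANSD and ADSD models, which SAP 4.4.10.1 describes only as similar to 4.3.2, keep the term. If the sponsor prefers the omission, SAP 4.12 should list it with a reason; that closes the documentation gap but forgoes the small gain.

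The cost is a wording change and one covariate correlated with baseline FEV1, in a model with two post-baseline visits. No new data are needed, and the 4.1.1 fallback already covers a missing % predicted value.

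Keep Day 1 pre-dose as baseline for the main FEV1 analysis. If wanted, add a sensitivity analysis using Visit 1 FEV1 where Day 1 is missing, stating which value applies after a run-in retest.
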